### **Protections Against Risks**

This study will be conducted according to good clinical practice (GCP) guidelines and with utmost concern for the participant's well-being. Appropriate safeguards will be used to minimize pain or discomfort associated with study participation and involve careful subject screening and monitoring. Procedures to minimize risks identified in the previous section are outlined below.

*Internal metal during MRI scanning:* The MRI Safety Screening Form will be used to screen for any internal or external ferromagnetic objects. If not removable, such objects would represent a basis for study exclusion. Participants will also be screened using the SAFESCAN® ferromagnetic detector to assure that they have no metal on or in their persons.

*Assessment of traumatic event exposure:* Participants will be instructed that they are free to refuse to respond to any items if they are not comfortable discussing them. Additionally, the trauma assessment interview (NSA) is worded with dichotomous questions so that the participant only has to answer yes or no to a series of questions. Additionally, if in ascertaining a participant's current condition, the need for clinical intervention is determined, the appropriate mental health referral will be arranged.

*Procedures for suicidal participants:* Individuals who are actively suicidal, defined as intending to hurt or kill themselves in the acute time frame, will be referred to the UAMS ER. The treatment response may include hospitalization. These participants will be ineligible for further study participation.

*Distress during the stress/trauma imagery task:* First, any history of claustrophobia would be assessed with participants acclimated to the scanner environment using a MR simulator to assess and minimize anxiety. Participants will be instructed that they are free to withdraw from study participation at any time, with their refusal to continue having no effect on medical care associated with UAMS. Second, numerous past studies have used script-driven imagery procedure for generic stress induction or trauma-specific stress induction, and while the protocol is successful in inducing either generic or trauma-specific distress, the distress is temporary and no adverse events have been noted. Third, participants are instructed that they can stop the task at any time without negative consequence to them.

*Personal health information/Loss of confidentiality:* To protect the identity of research volunteers, contact information will be stored in a separate file and in a locked cabinet from experimental data forms. All experimental data will be de-identified using an alphanumeric study code rather than a name or other identifying information. All data collection forms will be stored in a password-protected cabinet behind a locked office. Computer data records will be stored in password-protected network drives. Data will be stripped of all identifiers, including the stripping of facial features from the anatomical MRI data. All participants will receive a Notice of Privacy Practices, outlining the procedures UAMS investigators use, when they sign informed consent and the HIPAA agreement.

### **Potential benefits of the proposed research to the subjects and others**

There are no direct health benefits to participating subjects. However, the potential benefits of this research to society are major in terms of improving the ability to consolidate fear extinction learning memories.

### **Importance of the Knowledge to be Gained**

The goal of this program of research is to better understand how the brain encodes emotional distress upon exposure to trauma reminders and provide proof-of-concept data that neurofeedback can modulate this network and potentially boost existing therapy efficacy.

### **X. Outcome Measures**

Data will be collected from living human participants through clinical interview, self-report questionnaires, behavioral measures, and MRI scanning. Data for the project will be obtained specifically for research purposes.

### **XI. Data Handling and Recordkeeping**

The PI will carefully monitor study procedures to protect the safety of research subjects, the quality of the data and the integrity of the study. All study subject material will be assigned a unique identifying code or number. The key to the code will be kept in a locked file in the principal investigator's office. Only Drs. [name], [name] and [name] and the appropriate research coordinators will have access to the code and information that identifies the subject in this study.

### **XII. Statistical Plan**

#### **Power analysis**

A sample size of 10 for the pilot stage will provide sufficient preliminary data and experience implementing this technology to proceed to the implementation stage. Assuming large effect sizes, a sample size of 17 during the implementation stage should provide power  $> .8$  to detect the hypothesized within-subject effects (i.e., changes in brain activity and emotional arousal between the decrease – increase – decrease neurofeedback phases).

#### **Data analysis**

Image processing will be performed in AFNI. Standard preprocessing steps (motion correction, slice timing correction, noise filtering) will be applied, and then analyses will test hypotheses.

We would use a data-driven, model-free, approach towards identifying idiosyncratic brain mechanisms mediating emotional arousal upon exposure to trauma cues. This would use the whole-brain (i.e., voxel-wise) feature space (~50,000 voxels) in fitting the computational model. The fitted Q iteration algorithm (Reidmiller, 2005) would be fit to these data, such that the timeseries of activity for each voxel are used as input features with which to predict subsequent values of SCR. Cross-validation within- and across-participants would identify the

non-linear combination of the voxels whose timecourse of activity scales with the magnitude of the concurrent SCR response. In the neurofeedback phase, this fitted model would be computed on the observed brain states to provide feedback of the participant's current brain state with respect to the modeled target brain state. We would compare mean brain state activation and SCR response during neurofeedback phases using repeated measures GLMs for the within-subject manipulation of instruction (decrease – increase – decrease). Cluster level thresholding would be used to correct for multiple comparisons during the fMRI analyses, FDR would control for multiple comparisons during the SCR analyses.

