*Real-time fMRI and neurofeedback.*

*Modeling building phase.* The first phase of the MRI acquisition would consist of a single 3 min presentation of the stress/trauma script followed by a 3 min presentation of the neutral script (with the order counterbalanced across participants). In between the stress/trauma script and neutral script, there would be an emotion rating period, during which the participants indicate on a 9 pt Likert scale their anxiety and vividness of the imagery. Skin conductance response (SCR) will be recorded using BIOPAC's psychophysiological monitoring equipment. A series of electrodes placed on the participant's skin will measure SCR and provide an objective measure of physiological arousal. A subsequent reinforcement learning algorithm, fitted Q learning, would be applied to these joint fMRI and SCR data to identify distributed patterns of co-activated brain regions that specifically encode high emotional arousal (i.e., high SCR) to the stress/trauma memory. The resulting idiosyncratic brain map would inform the neurofeedback phase in the next three runs. This phase will take approximately 6 minutes.

*Neurofeedback phase.* In this phase, participants would undergo three additional 3 min presentations of the stressful/traumatic script; however, they would also concurrently be given neurofeedback to up- or down-modulate the identified brain network. In this neurofeedback phase, participants would be given visual feedback of the current state of their brain with

respect to the desired brain state (based on the computational model). In order to demonstrate a causal relationship between the brain state and emotional arousal, we would alternate between instructions to decrease the brain state (during which we expect to see decreased SCR), increase the brain state (during which we expect to see heightened SCR), and then decrease the brain state again. The sequence of manipulations would always be decrease – increase – decrease so that participants always end during a phase attempting to decrease emotional arousal. Also note that other experiments have used neurofeedback to modulate pain and both increase and decrease pain in order to demonstrate experimental control of pain through manipulation of the identified brain regions (deCharms, et al., 2005). This phase will take approximately 18 minutes.

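### Instruction is tied to run order and no contrast is named, so on its natural reading the test of modulation can be significant from habituation alone

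*Combined protocol and SAP*

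**What the plan says.** Section V, fMRI Procedures, fixes the order of the neurofeedback runs for everyone: "The sequence of manipulations would always be decrease – increase – decrease". The stated reason is that participants should finish on a decrease run. The stimulus does not change: "participants would undergo three additional 3 min presentations of the stressful/traumatic script", after one presentation already given in model building. Counterbalancing is described only for the stress/trauma script against the neutral script. The same section presents the alternation as the means of showing that brain state causes arousal, and it says that participants acquire control by trial and error as they go.

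Section IV gives a directional hypothesis: arousal goes up when the network is driven up and down when it is driven down.

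Section XII, Data analysis, gives the test: "We would compare mean brain state activation and SCR response during neurofeedback phases using repeated measures GLMs for the within-subject manipulation of instruction", with the three phases then listed in brackets. It names no contrast, direction, or run or time term. FDR is specified for the SCR analyses and cluster thresholding for the fMRI analyses. The Power analysis section refers to "changes in brain activity and emotional arousal between the decrease – increase – decrease neurofeedback phases" and likewise names no contrast.

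**The concern.** Runs 2, 3 and 4 are always decrease, increase and decrease, so any comparison of instructions is also a comparison of run positions. A repeated-measures GLM with three levels gives a 2-df test that the run means are equal. A steady fall in SCR or brain state as the script is replayed makes those means unequal even if instruction does nothing. FDR and cluster thresholding deal with the number of tests, not with an order effect.

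This comparison is the only group test stated for Aim 2, and it serves both outcomes. A significant result would be offered as evidence of causal modulation, although the same p-value could come from repetition. The reversal order already allows a better test, because an increase run placed between two decrease runs can be compared with their average. The plan does not say that this comparison is the one intended.

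**Working it through.** **Inputs.** From the documents: n = 17; three runs in fixed order; "Assuming large effect sizes", with no number; power above 0.8. Assumed, because the documents do not give them: two-sided 5% level; run SD 1; equal correlation ρ between runs (0.5, with 0.3 and 0.7 as a range); linear decline of b SD per run; large meaning a standardised paired effect of 0.8, or f = 0.4 for a three-level F test. Simulations use 40,000 trials per scenario.

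**1. The plan's own figure.** Paired t test, 16 df, non-centrality 0.8 × √17 = 3.30: power 0.87. The effect detectable with 80% power is 0.72. For a three-level F test, λ = 17 × 3 × 0.4² / (1 − ρ) = 8.16 / (1 − ρ), which gives power 0.84, 0.94 and 0.996 at ρ = 0.3, 0.5 and 0.7 (0.68 at ρ = 0). The stated power is reproduced under the usual readings.

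**2. Three-level test under habituation alone.** Run means are 0, −b, −2b. Their deviations from the average are b, 0, −b, with sum of squares 2b². So λ = 17 × 2b² / (1 − ρ), which is 68b² at ρ = 0.5, referred to F(2, 32).

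| b (SD per run) | λ at ρ = 0.5 | rejects, ρ = 0.5 | rejects, ρ = 0.3 | rejects, ρ = 0.7 |
|---|---|---|---|---|
| 0 | 0 | 5% | 5% | 5% |
| 0.1 | 0.68 | 10% | 9% | 14% |
| 0.2 | 2.72 | 27% | 21% | 43% |
| 0.3 | 6.12 | 55% | 41% | 78% |
| 0.4 | 10.88 | 81% | 66% | 96% |

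At b = 0.4 and ρ = 0.5 the first-to-last change has standardised size 2b / √(2(1 − ρ)) = 0.8, the same size taken above as large for the effect of interest.

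**3. How often this would look like the hypothesis.** Linear decline puts the first decrease run highest and the second lowest. In simulation at ρ = 0.5, the test is significant with the increase run highest in 2.2%, 3.5%, 4.1% and 3.3% of trials for b = 0.1, 0.2, 0.3 and 0.4.

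**4. The reversal contrast.** L = Run 3 − (Run 2 + Run 4)/2. Under linear decline its mean is −b − (0 − 2b)/2 = 0. Simulated rejection is 4.8–5.2% in every linear scenario, about 2.5% in the hypothesised direction. As a 1-df contrast it needs no sphericity assumption.

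**5. Power for a true effect of 0.8 SD (run means 0, 0.8, 0; ρ = 0.5).**
- Contrast: variance (1 + ¼ + ¼)(1 − 0.5) = 0.75, SD 0.866, standardised effect 0.8 / 0.866 = 0.92, power 0.95. It stays at 0.95 with linear habituation of 0.3 or 0.4 SD per run added.
- Three-level test: sum of squares 0.8² × 2/3 = 0.427, λ = 17 × 0.427 / 0.5 = 14.5, power 0.91.

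The 0.95 here and the 0.87 in step 1 are not in conflict. The first takes 0.8 in units of the run SD, the second 0.8 in units of the SD of the tested difference.

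**6. Non-linear drift, no instruction effect (ρ = 0.5).**
- Early drop that levels off (starting at 1 SD and halving each run): the contrast rejects 8.6%, of which 0.6 percentage points lie in the hypothesised direction.
- No change until a drop of h in the last run only: L has mean h/2. For h = 0.4 or 0.8 SD it rejects about 15% or 43%, practically all in the hypothesised direction. The three-level test rejects 35% or 91%.

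**The case against.** The Data analysis section does not mention an omnibus or 2-df test. It names the factor as instruction, which takes two values. If the authors meant increase against pooled decrease, that is the contrast in step 4 and linear habituation already cancels. This stands: what the documents show is an unspecified contrast, not a wrong one. The three-level reading is the natural one because all three phases are listed as the manipulation, but it remains a reading.

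A reader might also infer that the plan would falsely claim modulation in 27–81% of studies. The documents do not support that. Those rates count detections of a real difference between runs, and the hypothesis has a direction that linear habituation contradicts in the first pair. With the means inspected, the misleading pattern appears in about 2–4% of trials. Increase against the second decrease alone would be falsely significant in 12%, 21% or 34% of trials at 0.2, 0.3 or 0.4 SD per run (nominal 2.5%), but that is a pairwise test the plan does not name, and the figures are before FDR.

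The size, shape and presence of habituation are all assumed, and at 0.1 SD per run the inflation is modest. This is also a small proof-of-concept study. These points lower the practical harm. They do not remove the need to name the test, since protection should not depend on how the means happen to be read afterwards.

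**Conclusion.** The point holds as a gap in specification with a measurable consequence. The order is fixed, the script is repeated and no contrast is stated. On the three-level reading, significance alone cannot separate instruction from repetition: 10–81% rejection for linear declines of 0.1–0.4 SD per run at n = 17 and ρ = 0.5, with the same picture at ρ = 0.3 and 0.7. The reversal contrast removes the linear part and gains a little power.

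Two stronger conclusions are not supported. First, the contrast does not make the causal inference safe. It protects against linear drift, and against early-then-levelling drift in the hypothesised direction, but not against a fall concentrated in the last run. Trial-and-error learning, which the protocol itself describes, is another reason not to take a linear time course for granted. Second, the sample size is not shown to be wrong: the claim that "a sample size of 17 during the implementation stage should provide power" above 0.8 is reproduced.

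**What to change.** In section XII, Data analysis, make one pre-specified test of modulation for each outcome (brain state and SCR): the directional within-subject contrast Run 3 minus the mean of Runs 2 and 4, by a t test on n − 1 df (16 with 17 participants). State the level and sidedness. Report Run 3 − Run 2, Run 3 − Run 4 and Run 2 − Run 4 beside it. Claim modulation only if the contrast is significant and positive and the increase run's mean exceeds both decrease runs' means.

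Requiring each pairwise difference to be significant would hold the late-drop error at or below 2.5%. However, power for a 0.8 SD effect would be 79% without habituation and 49% or 35% with 0.3 or 0.4 SD per run. It is therefore not proposed as the primary rule.

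Add a limitation: a fixed order cannot rule out non-linear time or practice effects. The condition on the means does not close this gap, because after a drop in the last run only, the increase run still exceeds the first decrease run about half the time by chance. Temper the causal wording in section V, fMRI Procedures, to match.

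Optionally, say in the Power analysis section that the figure refers to this contrast (0.87 at standardised effect 0.8, 80% at 0.72, n = 17). That is a clarification, not a correction.

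The cost is a few sentences. Run order, scanning and sample size are unchanged.

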## **IX. Risks and Benefits**

### **Potential risks**

*Internal metal during MRI scanning:* One potential safety concern is participant internal metal during MRI scanning, which can be painful and dangerous.

*Assessment of mental health and traumatic event exposure:* One potential psychological risk of the proposed study is the possibility that some participants might experience distress or become offended when asked questions pertaining to victimization and mental health history. Many people assume that asking such questions produces substantial distress, particularly in research settings. However, the empirical literature suggests that this risk is minimal, and that individuals with traumatic event histories actually report obtaining positive benefits from their participation in studies where traumatic event history is assessed (Griffin, Resick, Waldrop, & Mechanic, 2003; Newman, Walker, & Gefland, 1999).

*Assessment of suicidal ideation:* During the clinical interview (SCID) in the depression module, questions regarding suicidal ideation are asked. This may elicit distress from participants; however, there is a specific protocol should a participant report suicidal ideation, intent, or plan, and a protocol to decrease distress, described below. Individuals meeting criteria for current major depression will be excluded from the study, further decreasing the likelihood of reported suicidal ideation.

*Distress during the stress/trauma imagery task:* Another potential risk is that the script-guided imagery procedure will elicit anxiety/distress, in addition to the MRI environment itself. Participants are able to quit the task at any time by indicating to the MRI coordinator(s) that they wish to do so.

*Personal health information/Loss of confidentiality:* With all research participation, there is a risk that personal information obtained from research participants will be mishandled, and confidentiality may be compromised.

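### The repeated measures GLM, in its usual form, keeps only women with all three feedback runs; loss could bias the increase contrast in either direction and lower power

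*Combined protocol and SAP*

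**What the plan says.** Section XII (Data analysis) gives one test for both outcomes, brain state activation and skin conductance: "We would compare mean brain state activation and SCR response during neurofeedback phases using repeated measures GLMs", with instruction (decrease, increase, decrease) as the within-subject factor. It names no analysis set, no rule for a missing or unusable run, no imputation and no model for incomplete data.

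Section XII (Power analysis) says that "a sample size of 17 during the implementation stage should provide power" above 0.8 "to detect the hypothesized within-subject effects (i.e., changes in brain activity and emotional arousal between the decrease – increase – decrease neurofeedback phases"). The basis is "Assuming large effect sizes", with no number. Section VI gives the same 17 as the enrolment target, so enrolled and analysed numbers coincide.

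Section V fixes the run order, with the increase run always second of three. Section IX names distress from the script procedure as a risk. It says "Participants are able to quit the task at any time by indicating to the MRI coordinator(s"), and later that "participants are instructed that they can stop the task at any time without negative consequence to them".

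**The concern.** A classical repeated measures GLM needs a value in every cell. A woman who stops after the increase run, or who loses a run to motion or signal failure, then leaves the whole comparison, although her other runs were observed. A woman with the first decrease run and the increase run already carries direct information on the hypothesis.

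Two things are at stake. In a sample of 17, each deletion costs visible power. And if the chance of stopping is related to arousal, which is itself an outcome, the women who remain are a selected group and the estimated contrast may be wrong. Because the task is designed to evoke distress and stopping is allowed, a link between arousal and stopping is plausible, though the documents do not demonstrate one.

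**Working it through.** **Inputs.** From the documents: n = 17, three feedback runs in fixed order, power above 0.8, a large effect. Assumed because not stated: two-sided alpha 0.05, the numerical effect size, the within-person correlation, and the number of and reason for incomplete sets.

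**1. The stated power.** For a paired contrast, power = P(|t| > t₀.₉₇₅,ₙ₋₁), where t is noncentral with n − 1 df and noncentrality dz√n. With dz = 0.8 and n = 17 the noncentrality is 0.8 × 4.123 = 3.30 and power is 0.872. The smallest dz that gives 0.8 is 0.72. A three-level repeated measures F test with f = 0.4 and λ = 3nf²/(1 − ρ) gives 0.838 at ρ = 0.3 and 0.941 at ρ = 0.5, but 0.683 at ρ = 0. The plan's figure is reproducible under ordinary assumptions.

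**2. Fewer women, same effect (dz = 0.8).**

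| Complete sets | 17 | 16 | 15 | 14 | 13 | 12 |
|---|---|---|---|---|---|---|
| Power | 0.872 | 0.848 | 0.821 | 0.790 | 0.754 | 0.714 |

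Under this assumption power passes below 0.8 at the third loss.

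**3. Selective loss.** Simulated trials, n = 17, each run with variance 1, correlation 0.5, contrast = increase run minus the mean of the two decrease runs, true value 0.80. The contrast has variance (1 − 0.5)(1 + 1/2) = 0.75, so SD 0.866 and dz = 0.80/0.866 = 0.92. Power with complete data is therefore about 0.95, higher than in step 1. With 3 of 17 women incomplete:

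| Who is incomplete, and what is lost | Complete-case estimate (power) | Mixed model estimate (power) |
|---|---|---|
| Random; last run | 0.80 (0.89 to 0.90) | 0.80 (0.95 to 0.96) |
| Highest in the increase run; last run | 0.65 to 0.66 (0.78 to 0.79) | about 0.80 (about 0.95) |
| Highest in the first decrease run; last run | 0.87 to 0.88 | 0.80 |
| Highest mean over the first two runs; last run | 0.76 | 0.81 |
| Highest underlying arousal level; last run | 0.80 to 0.81 | 0.85 |
| Highest in the increase run; the increase run itself | 0.64 (0.76) | 0.60 (0.74) |

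Ranges are repeat simulations. In the first five rows an unstructured covariance and a random intercept give much the same estimate; the last row was run with a random intercept.

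With selection on increase-run arousal, 1 or 2 stoppers give complete-case estimates of 0.74 and 0.70, with power about 0.91 and 0.85. With no true effect and 3 such stoppers, the two-sided error rate is 10 to 11% for complete cases and 5 to 6% for the mixed model.

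**4. Direction when individual effects vary.** In a second set-up, women differ in their true increase effect (mean 0.8, SD 1). The bias in the complete-case contrast is:

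| Stopping follows | 2/17 removed | 4/17 removed |
|---|---|---|
| Overall level, unrelated to effect | 0% | 0% |
| Overall level, correlation with effect +0.3 | −8% | −15% |
| Overall level, correlation with effect −0.3 | +8% | +15% |
| Failure to down-regulate in the first decrease run | +8% | +15% |
| Arousal in the increase run | −21% | −38% |

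The contrast is within-woman, so a generally high level cancels. Bias arises only where stopping is tied to the contrast, and its sign follows that tie.

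**5. Form of the mixed model.** A random intercept alone assumes that every woman has the same true effect. With individual effects of SD 0.8 and complete data, its error rate is 7.3%, against 4.7% for the paired contrast; with 3 stoppers it is 8.6%. An unstructured covariance does not make that assumption.

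**The case against.** The strongest reply is that nothing in the documents shows who would stop. Section IX reports that distress in past script studies was short-lived, without adverse events; the feedback runs last three minutes each; and Section VI excludes unstable women and those with major depression. Freedom to stop is an ethical safeguard, not evidence of selective dropout. This stands, and it is why the size is given as a range. It does not show that no run will be lost, and it says nothing of motion or signal failure.

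A reader might infer that the most aroused women will stop and that the increase effect is therefore biased toward zero. The documents do not support this. It requires stopping tied to a larger individual increase; other equally possible reasons give no bias or bias away from zero. A reader might also take deletion to be the plan's stated rule. It is the usual behaviour of the named method; the plan itself is silent.

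Finally, a mixed model is not a cure in every case. If stopping follows a woman's underlying arousal level, it drifts to about 0.85 while the complete-case estimate stays near 0.80. If the increase run is lost, it does no better than complete cases. Both limits stand. They call for a sensitivity analysis; they are not grounds for discarding observed runs.

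**Conclusion.** The concern holds in a limited form. The named method ordinarily discards women with an incomplete set of runs, stopping is allowed, and 17 has no margin. With 3 of 17 lacking the last run, correlation 0.5 and a true contrast of 0.80 SD, the complete-case estimate runs from about 0.66 to about 0.87 depending on why women stop. Power falls from about 0.95 to about 0.90 if loss is random and about 0.79 if it follows increase-run arousal. At dz = 0.8, three losses alone take power from 0.87 to 0.79. All of these rest on assumed inputs.

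No direction of bias is established. An upward bias would matter as much as a downward one in a study meant to give proof of concept. A change of method is worth making because it uses data already in hand and costs little; it is not a demonstrated correction for every pattern of stopping.

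**What to change.** In Section XII, Data analysis, replace the repeated measures GLMs with a linear mixed model for each outcome that uses every observed run: run/instruction as fixed effects, unstructured within-person covariance (not a random intercept alone), REML, and Kenward-Roger degrees of freedom. Report the number of missing or unusable runs by instruction, with reasons. Add a sensitivity analysis for arousal-related stopping, for example by shifting the unobserved values over a stated range and showing whether the conclusion changes.

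The cost is a few sentences in the plan and a little more analysis work in standard software. If all 17 women complete all three runs, the estimated run means and contrast are the same as those from the present plan. The plan should state the limit openly: the model removes bias only when stopping depends on observed runs, and does not correct for loss of the increase run itself or for stopping driven by unobserved arousal.
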